5.5.11.1 Record any adverse events

5.5.11.2 Record any changes to concomitant medications

5.5.12 Post-Study Survival Follow-Up ARMS A & B (questionnaires and WHO analgesic scale once yearly; survival, disease progression, SSE twice yearly)

- Survival status
- Disease progression
- Symptomatic-skeletal event
- WHO analgesic scale
- A subset of the following questionnaires will be used:
- BPI-SF, FACT-G, EPIC-26, FACIT-Fatigue, EQ5D, EORTC QLQ-30, STAI, CES-D, memory
- Modified Godin and other exercise questionnaire

6 ARM A: EXERCISE INTERVENTION (SOM: [Appendix 14](#))

6.1 Supervised Exercise Plan (Cycles 0-11)

The exercise intervention will include 48 weeks of aerobic and resistance training three times per week with the goal of delivering three moderate-to-vigorous aerobic training sessions and two structured resistance training sessions each week. A total of 88 supervised sessions should be completed within Year 1, in the event that the patient does not have any AEs that would prohibit him from reducing the number of exercise sessions. As long as the prescribed supervised dose is 88 sessions in Year 1, there is flexibility regarding the number of supervised sessions in a given week in Year 1.

Original Program: We strongly advise patients to adhere to the original program, with patients receiving three supervised exercise sessions in weeks 1-4 (Cycle 0), prior to the supervised exercise sessions tapering

throughout the program to two supervised sessions and one self-managed session for weeks 5-36 (Cycles 1-8) and one supervised training session and two self-managed sessions for weeks 37-48 (Cycles 9-11).

Flexible Entry: Although patients randomised to Supervised Exercise are **requested** to complete 3 supervised exercise sessions per week during Cycle 0 (totalling 12 supervised exercise sessions in this cycle), we recognise that some patients may require an 'easier' entry into the study in order to agree to enrol. This **flexible entry** option is permitted, where patients may complete a minimum of 1 to a maximum of 3 supervised sessions each week in Cycle 0, prior to joining the 'full program' from Cycle 1 onwards. However, while we allow the flexibility of less than 3 supervised sessions per week, those sessions will need to be made up later in Year 1 such that they complete the 88 sessions within Year 1. If using a flexible entry option, please prioritise the combined high-intensity interval training and resistance training sessions (Day 1 or Day 3 above) as it is easier to insert moderate-intensity continuous training sessions (Day 2) later in the program, when recovering missed supervised sessions. Examples of flexible entry plans are included in the SOM.

Exercise prescription will be tailored to the participant's baseline cardiopulmonary and strength assessments, and baseline conditions. The three training sessions each week will be **generally** structured as follows, with subtle alterations for variety, periodisation **and autoregulation**:

Day 1 - High load, low-volume resistance training and vigorous, high intensity interval aerobic

Day 2 - Moderate intensity continuous aerobic training

Day 3 - Moderate load and volume resistance training and vigorous, high intensity interval aerobic training

Exercise training will take the form of a periodised program. Training will be periodised within cycles of both 7 days (microcycle) and 28 days (mesocycle) duration. A periodised training approach allows training to be systematically organised into training phases to maximise the stimulus to physiological adaptation while reducing risk of injury, overtraining and staleness.

Within each week, Day1 training will involve high load and low volume resistance training in addition to high intensity interval aerobic training, the second day will consist purely of continuous aerobic training, and the third day will be moderate load and moderate volume resistance training and high intensity interval aerobic training. To achieve periodisation across the mesocycle, intensity of both aerobic and resistance training will increase with matching decreases in volume. On the first training day of each cycle the intensity will be dropped, volume increased and the pattern repeated across the cycle. For example, within each mesocycle training weight will progress linearly during the first 14 days, exercise volume will drop during days 15-21 and the cycle will finish with an unloading period from day 22-28.

6.1.1 Resistance Training

Resistance training exercises will be individually prescribed based on 1RM chest press, leg press and seated row assessments. Resistance training will consist of 2 to 4 sets at a load between 5 and 12 RM. For example, an 8RM is the weight that can be lifted only eight times. For non-athletes, there is little additional benefit performing resistance training sets to failure, so participants will be encouraged to finish the set one or two repetitions before neuromuscular failure.

During cycle 1 resistance exercise volume will be introduced incrementally, starting with 1 x 8RM. During subsequent cycles resistance training prescription will follow a standard linear progression as outlined in the SOM: [Appendix 14](#). Participants will complete a total of two resistance training classes per week with a minimum of 48 hours recovery between resistance training sessions. The first session (Day 1) will comprise high load, low volume exercise where the load will vary from 5RM to 8RM. The second session (Day3) will comprise moderate load, moderate volume exercise where the load will vary from 10RM to 12RM. Exercises will comprise both lower body and upper body exercises. Exercise prescription will be modified based on the site and severity of the metastases. A sample of resistance exercises that could be completed include:

Lower Body

Leg press
Leg Curl
Leg Extension
Lunges

Upper Body

Chest Press
Seated Row
Lat Pulldown
Shoulder Press

6.1.2 Aerobic Training

Aerobic exercise prescription will be prescribed and modified based on autoregulation. The Constant Load Exercise Test will be completed within 7 days on or after Day 1 of Cycles 0, 1, 2, 3, 4, 5, 6, 7, 8, 9, 10, and 11. Aerobic exercise prescription will take the form of high intensity interval training (HIIT) and continuous exercise.

HIIT involves alternating periods of work and active rest usually (but not always) on a ratio of 1:1 with work intervals of anywhere between 20 seconds and 4 minutes. This form of exercise prescription is designed to minimise the duration of exercise sessions by focusing on short bouts of high intensity aerobic. Such exercise has been demonstrated to be safe and highly effective in a range of patient populations including those with established cardiovascular disease and advanced metabolic syndrome⁴⁷ and may be more appropriate for advanced cancer patients who experience fatigue and discomfort with extended periods of long duration, low intensity aerobic exercise. HIIT sessions will be completed on Day 1 and Day 3 of each week following completion of prescribed resistance exercises. HIIT sessions will last for 20 minutes with a target intensity of $\geq 85\%HR_{max}$. Continuous vigorous aerobic exercise will be completed on Day 2 of each week for 35 minutes at an aerobic intensity of 60-85% HR_{max}.

Aerobic exercise training can be completed on a variety of exercise equipment including treadmill, cycle ergometer, cross trainer, rowing ergometer and arm crank ergometer. Decisions regarding individual exercise prescription will be made based on the site and severity the metastases.

6.1.3 Modifications to Exercise Prescription

The exercise physiologist /therapist leading the program may make amendments to the training protocol on an individual basis based on **autoregulation of training** and the site of the metastasis.

Autoregulation of training will be applied to enhance adherence and tolerance to the prescribed protocol. Using this method, the participant, in conjunction with their exercise trainer has the potential to adjust intensity and volume of the session according to their perceived capacity at that time. This is proving successful with other advanced cancer patients because it allows for auto-regulation of training load to account for fluctuations in fatigue state, changes in treatment phase, recovery capacity and scheduling commitments. For example, on a day when the participant feels highly fatigued they may elect to complete their resistance exercises as planned but postpone the aerobic exercise component to be done at home later in the week. The basis of auto-regulation training is that the participant achieves the target exercise mode, volume and intensity across any 1 or 3 cycles. Monitoring of autoregulation will be managed through review of the data on exercise volume completed, entered into the database by the exercise physiologist, trainer, etc. During the transition period participants will take responsibility for their own data entry at home, which will be provided to the exercise physiologist and added to our database. Participants will be provided with heart rate monitors to wear at home to monitor adherence to aerobic exercise prescription and from that record their average and maximum heart rate values, RPE, and exercise duration. Participants will record volume of resistance training completed through reporting number of sets, repetitions, and weight lifted.

Exercise prescription should also be modified in all participants based on the location and severity of bone metastases. A choice of exercises is available for both aerobic and resistance training. Decisions about appropriate exercise prescription should be taken by the exercise physiologist /therapist in consultation with the treating medical physician. Exercise selection should be modified where necessary throughout the program in response to participant feedback (i.e. tolerability, discomfort, bone pain, etc.). Any exercise which causes a participant issues should be removed from the program and replaced with one that is more appropriate and well tolerated.

Guidelines for exercise prescription based on site of metastases is provided in [Table 3](#) below. All decisions must

be taken in consultation with the participant's treating medical physician and the ECC.

Table 3. Modification to Exercise Prescription by Site of Bone Metastases

Metastases Site	Exercise Mode					
	Resistance			Aerobic		Flexibility
	Upper	Trunk	Lower	WB	NWB	Static
Pelvis	√	√	√**		√	√
Axial Skeleton (lumbar)	√		√		√	√***
Axial Skeleton (thoracic/ribs)	√*		√	√	√	√***
Proximal Femur	√	√	√**		√	√
All regions	√*		√**		√	√***

√ = Target exercise region;

* = exclusion of shoulder flexion/extension/abduction/adduction – inclusion of elbow flexion/extension;

** = exclusion of hip extension/flexion – inclusion of knee extension/flexion;

*** = exclusion of spine/flexion/extension/rotation;

WB = weight bearing (e.g. walking);

NWB = non-weight bearing (e.g. cycling);

6.1.4 Transition to self-managed exercise program

After 9 cycles, participants will be transitioned to self-management across a 3 cycle period. The number of supervised exercise classes will be tapered from 2 classes/week during cycles 1-8, to 1 supervised training session during cycles 9, 10 and 11. Aerobic exercise will be tapered first followed by resistance training classes. Throughout the supervised intervention period (Cycles 0-11), the intervention arm will complete the Constant Load Exercise test (within 7 days on or after Day 1 of Cycles 0-11) and 1RM strength testing (within 7 days on or after Day 1 of Cycle 9) to monitor progression and adherence to the prescribed protocol and inform continued progression of exercise prescription. Participants will be provided with heart rate monitors to wear for the duration of the supervised intervention (cycles 0-11) to monitor aerobic exercise prescription. The specifics of the self-managed program can be highly variable so long as across a given one to three cycle period the participant averages the equivalent of 75 minutes of vigorous aerobic exercise and two resistance training sessions each week. The key criteria for adherence and compliance will be that the participant meets the target aerobic and resistance training as per their individual exercise prescription. Participants will be reassessed within 7 days on or after Day 1, Cycle 12, following which they will be instructed to continue with self-managed exercise until Day 1, Cycle 24, disease progression, or patient mortality, whichever occurs first. The intervention period will cease at Cycle 24.

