5.5.4.6 Perform 400m walk test (Day 2)

5.5.4.7 Perform 1RM strength assessment chest press, leg press, seated row, and leg extension (Day 2)

5.5.4.8 Complete Constant Load Exercise Test (Day 2).

NOTE: Please see [Table 1](#), footnote 14 for adverse events collection & reporting, and [Table 1](#), footnote 15 for medication collection & reporting.

5.5.5. Cycle 0 (within 7 days on or after Day 1) – One to three Exercise Training Visits per 7 days for ARM A

Exercise session (1 to 3 supervised exercise sessions per 7 days – refer to Section 6.1 for details)

▪ **Day 1**

- **Assessment:** Bone pain (VAS), Fatigue (VAS), resting heart rate, resting blood pressure, and record any new adverse events or changes to medication.
- **Warm up:** 5 minutes cycling at a light to moderate intensity
- **Exercise:** High load, low volume resistance training; high-intensity interval aerobic training.
- **Outcomes:**
 - Resistance Exercise: Number of sets, number of repetitions, weight lifted.
 - Aerobic Exercise: Work interval, rest interval, number of repetitions, RPE achieved.
 - Sessional Data: Sessional RPE, post-aerobic heart rate, post-session blood pressure

- **Cool down:** Trunk flexion and extension exercises and static stretching
 - **Day 2**
 - **Assessment:** Bone pain (VAS), Fatigue (VAS), resting heart rate, resting blood pressure and record any new adverse events or changes to medication.
 - **Warm up:** 5 minutes cycling at a light to moderate intensity
 - **Exercise:** High intensity continuous aerobic training
 - **Outcomes:**
 - Aerobic Exercise: Work interval, rest interval, number of repetitions, RPE achieved.
 - Sessional Data: Sessional RPE, post-aerobic heart rate, post-session blood pressure
 - **Cool down:** Trunk flexion and extension exercises and static stretching
 - **Day 3**
 - **Assessment:** Bone pain (VAS), Fatigue (VAS), resting heart rate, resting blood pressure and record any new adverse events or changes to medication.
 - **Warm up:** 5 minutes cycling at a light to moderate intensity
 - **Exercise:** Moderate load and volume resistance training; high-intensity interval aerobic training
 - **Outcomes:**
 - Resistance Exercise: Number of sets, number of repetitions, weight lifted.
 - Aerobic Exercise: Work interval, rest interval, number of repetitions, RPE achieved.
 - Sessional Data: Sessional RPE, post-aerobic heart rate, post-session blood pressure
 - **Cool down:** Trunk flexion and extension exercises and static stretching

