Patients are permitted to take holidays however must commit to self-management of exercise during this period. During pre-planned or spontaneous holidays for patients (while on-trial), and/or due to unforeseen circumstances precluding attendance to a supervised session (such as an illness to spouse, or conflicting medical appointment), patients may complete a self-managed session under the strict guidance and overview of the site's research coordinator and exercise physiologist (to be recorded). If this occurs, a self-managed session replacing a supervised session in this way must be recorded in REDCap. If no session is performed to recover the missed session (without any adverse event, or other justifiable reason), this will be recorded in REDCap. During holidays, if patients do not have access to exercise facilities or equivalent items of use, these can be recovered during subsequent weeks within the Year it occurs (as is the definition of autoregulation; to ensure the overall program is upheld). This will be monitored by the Study and Exercise Coordination Centres during routine monitoring visits.

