12.11.3 Per Protocol Analyses

Secondarily, we will conduct analyses using a per-protocol analysis to investigate the possibility of a dose

response or threshold effect. Participants who attend 80% or more of the supervised exercise sessions will be considered to have complied with the protocol.

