15.8 Exercise Training Data Collection and Management

Sets, Repetitions and Weight Lifted (Resistance Exercise), as well as Duration, Recovery, Repetitions and RPE (Aerobic Exercise) data will be collected for each exercise performed. Pre-session Bone Pain, Pre-session Fatigue Levels, Post-Aerobic HR, and Post-Session RPE data will be collected for the session overall. All data entries will be monitored by the ECC to ensure high quality data. Exercise data will be recorded and reported via PhysiTrack (an online form). Sessional data will be recorded and reported via REDCap (an online form). This will ensure all data is logged and maintained for each participant accordingly. Please pay careful attention to the data you and your patients enter.

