15.9 Self-Management of Exercise Data Collection and Management

Participants will be provided with heart rate monitors to wear at home to monitor adherence to aerobic exercise prescription (heart rate average and maximum) and record session RPE, exercise duration, exercise intensity,

number of repetitions and recovery periods used. Participants will also record the volume of resistance training completed through reporting number of sets, repetitions, and weight lifted. These data will be reported through PhysiTrack (preferred) or on a written form (SOM: [Appendix 16a](#)) to be provided to the exercise professional at the on-site visits. **The exercise professional is responsible for entering written forms into PhysiTrack** on behalf of the participant, should this option be used. Select sessional variables will be entered into the online database (REDCap) and will also be monitored by the ECC to ensure high quality data and used for reporting purposes.

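### Section 6.1.4 judges compliance by exercise dose achieved, but the per-protocol analysis in 12.11.3 uses one 80% cut on supervised attendance, with no period named, although dose is logged

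*Combined protocol and SAP*

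**What the plan says.** **Dose as the criterion.** Section 6.1.4 lets the self-managed programme vary so long as, over one to three cycles, "the participant averages the equivalent of 75 minutes of vigorous aerobic exercise and two resistance training sessions each week". It then says: "The key criteria for adherence and compliance will be that the participant meets the target aerobic and resistance training", according to the individual prescription. Section 6.1.3 sets a similar standard for autoregulated training: target mode, volume and intensity are to be reached across 1 or 3 cycles.

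**Attendance as the criterion.** Section 12.11.3 says: "Participants who attend 80% or more of the supervised exercise sessions will be considered to have complied with the protocol". Its stated purpose is to look for a dose response or a threshold effect. Section 6.1.5 defines attendance as in-person sessions attended over planned supervised sessions. Section 12.4 adds secondary analyses of non-compliance and of the number of supervised sessions completed. Section 12.8 plans a biomarker dose-response analysis against compliance without saying which definition applies.

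**Where the two part company.** Under 6.1.3 a tired participant may do his resistance work and "postpone the aerobic exercise component to be done at home later in the week". Under 6.1.5 a man on holiday or otherwise unable to attend may exercise on his own, and "a self-managed session replacing a supervised session in this way must be recorded in REDCap".

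**What is recorded.** For supervised sessions, 5.5.5 to 5.5.7 list sets, repetitions and weight, and "Aerobic Exercise: Work interval, rest interval, number of repetitions, RPE achieved". Section 15.8 adds duration and recovery, and says: "Pre-session Bone Pain, Pre-session Fatigue Levels, Post-Aerobic HR, and Post-Session RPE data will be collected for the session overall". Section 15.9 names average and maximum heart rate for home sessions. Section 6.1.2 sets aerobic intensity as a percentage of maximum heart rate.

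**The concern.** Attendance and dose can diverge under the protocol's own rules. Section 6.1.5 says fatigue should lead to an adjusted session and not a missed one, so attendance can hold up while dose falls. An attended session counts in full whatever was done in it. A permitted self-managed replacement scores as missed, and routine self-managed sessions never count.

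At stake is the reading of the secondary compliance analyses. The per-protocol group could leave out men who did most of the planned exercise and take in men who did about half of Year 1. A single cut gives one two-group contrast. It shows neither a gradient nor where a threshold lies. The power statement in 12.2, for 371 compliant men against 412 controls, also depends on who counts as compliant.

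**Working it through.** **1. Planned sessions in Year 1 (section 6.1).**
- Supervised: 4 weeks × 3 + 32 weeks × 2 + 12 weeks × 1 = 12 + 64 + 12 = 88. This reproduces the protocol's figure.
- Self-managed: 32 × 1 + 12 × 2 = 56.
- Total: 144, which equals 48 weeks × 3. Supervised share: 88/144 = 61.1%.

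**2. Prescribed aerobic minutes in Year 1 (6.1.2; division of sessions from 5.5.5 to 5.5.7).** A week has 20 + 35 + 20 = 75 minutes, so 48 × 75 = 3,600.
- Supervised, Cycle 0: 4 × 75 = 300.
- Supervised, Cycles 1-8 (two interval sessions a week): 32 × 40 = 1,280.
- Supervised, Cycles 9-11 (one a week): 12 × 20 = 240.
- Share: 1,820/3,600 = 50.6%.

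**3. Who is classed how, on the Year 1 denominator.** 0.80 × 88 = 70.4, so 71 sessions are needed.

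| Man | Attendance | Class under 12.11.3 | Share of 144 sessions done |
|---|---|---|---|
| 71 supervised, 0 at home | 71/88 = 80.7% | Compliant | 71/144 = 49.3% |
| 70 supervised, 56 at home | 70/88 = 79.5% | Non-compliant | 126/144 = 87.5% |

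**4. Over 24 cycles.** Section 6.1.8 gives about one supervised session per cycle from Cycle 12, so about 12 in Year 2. The weekly number of sessions in Year 2 is not stated; I assume 2 to 3.

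| Year 2 sessions per week | Total planned | 88 supervised | 100 supervised |
|---|---|---|---|
| 3 | 144 + 144 = 288 | 30.6% | 34.7% |
| 2 | 144 + 96 = 240 | 36.7% | 41.7% |

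The choice of period changes the classification. If the first man attends none of the 12 Year 2 sessions, he has 71/100 and becomes non-compliant. If the second attends all 12, he has 82/100 and becomes compliant.

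**5. Time needed to qualify.** On the original schedule a man has had 12 + 29 × 2 = 70 supervised sessions by the end of week 33, so nobody who dies before then can reach 71. Under the design's exponential model (control median 33.5 months; 33 weeks ≈ 7.59 months), the proportion dying by then is 1 − 2^(−7.59/33.5) = 14.5% at the control hazard, and 1 − 2^(−0.78 × 7.59/33.5) = 11.5% at the target hazard ratio. This only illustrates the design model; it does not forecast deaths in this selected population.

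**6. Heart rate.** Interval sessions in Year 1 number 48 × 2 = 96, of which 4 × 2 + 32 × 2 + 12 × 1 = 84 (87.5%) are supervised. For these, 15.8 names only a post-aerobic heart rate.

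**The case against.** The sentence in 6.1.4 follows the self-managed weekly target, in a section on transition, and can be read as covering that phase only. Section 13.1.1 defines the study intervention as supervised exercise, and supervised sessions hold 84 of the 96 Year 1 interval sessions and, on the same days, 84 of the 96 resistance sessions. Attendance is therefore a coherent measure of the intensive component. This softens the conflict. It does not remove it: 6.1.3 sets a similar dose standard, and if 6.1.4 covers home exercise alone, no home-exercise criterion enters any analysis.

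A reader might infer several stronger things that the documents do not support.
- **That the dose-response question cannot be answered.** Resistance volume, intervals, duration and RPE are logged, and 12.4 already plans a graded analysis by number of supervised sessions. The dose measure lacks pre-specification, not data.
- **That supervised sessions are only about a third of the programme.** That holds only over 24 cycles with an assumed Year 2 frequency. In Year 1 the share is 61%.
- **That a compliant man may have done only a quarter of the exercise.** That sets a Year 1 attendance rule against a 24-cycle total, and the classification reverses with 100 supervised sessions as denominator.
- **That autoregulation deletes the aerobic part.** Section 6.1.3 postpones it.
- **That in-exercise heart rate is not captured under supervision.** Monitors are worn in Cycles 0-11 (6.1.4). The session lists in 5.5.6 and 5.5.7 also omit average and maximum heart rate for home sessions, where 15.9 shows they are recorded. Absence from a list is weak evidence, and the operations manual is not available here.
- **That a null survival result would leave delivery unknown.** CPET, 1RM and the 400m walk are measured in both arms, and the first interim analysis in 12.12 tests for an effect on strength and walking.

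**Conclusion.** The point holds as a defect in the secondary compliance analyses. Two definitions of compliance stand unreconciled, and the one chosen for analysis ignores the 56 of 144 Year 1 sessions done at home and all variation within a session. On the Year 1 denominator it can class 49% of planned sessions as compliant and 87.5% as non-compliant. These are boundary cases; the documents do not show how often they would occur. The Year 1 figures rest on the original schedule in 6.1; the 24-cycle range of 31% to 42% rests on the assumed Year 2 frequency and on whether Year 2 supervised sessions count. A single cut is a weak test of the stated aim, and 12.11.3 does not address the fact that compliance builds up after randomisation while survival is counted from it. The intention-to-treat primary analysis is unaffected.

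**What to change.** 1. Reconcile 6.1.4 with 12.11.3, and use one definition of compliance in 12.4, 12.8 and 12.11.3, with the period named (12 or 24 cycles).
2. Make the main measure a graded ratio of delivered to prescribed dose over supervised and self-managed sessions, from the PhysiTrack and REDCap logs: resistance as sets × repetitions × load, aerobic as minutes completed with the recorded intensity. State which prescription is the denominator; if it is lowered whenever a session is autoregulated, the ratio hides the shortfall.
3. Keep 80% attendance as a sensitivity measure.
4. Use a landmark or time-updated analysis, so that early deaths are not scored as non-compliance. A landmark drops deaths before it, so its timing should be fixed in advance.
5. In 15.8, list average and maximum heart rate for supervised aerobic bouts, as 15.9 does for home sessions, or state that RPE is the intensity measure. These fields describe intensity; they do not give minutes at target for interval work.

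The cost is analysis-plan text and, if heart rate is chosen, two fields from monitors already worn in Cycles 0-11. The downsides are that home logs are self-reported, which is why attendance stays as a check, and that delivered dose is confounded by health. The analysis should therefore stay secondary and exploratory.
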